### 5 STUDY DESIGN

This is an intervention study at Ola During Children's Hospital

#### 5.1 Population

##### 5.1.1 Inclusion criteria

In order to be eligible to participate in the interventional study, a patient must meet the following criteria:

- Newborn admitted to Ola During Children's Hospital
- Fulfills inclusion categories defined in Table 1.
- Written informed consent of the patient or his/her formal representative.

##### 5.1.2 Exclusion criteria

- When informed consent cannot be obtained
- Newborns with fatal congenital diseases
- Newborns with critical conditions (breathing disorder, sepsis)
- Newborns under 800g over 2000g
- Fulfills one or more of the two inclusion categories defined in Table 2.

**Table 1.** Inclusion categories

Inclusion criteria	Case Definition
Birth weight	Newborns from 800g to 2000g

Table 2.

Exclusion criteria	Case definition
Weight	< 800 > 2000g
Baby's conditons	Breathing disorders, sepsis, and fatal congenital diseases

### 1.1 Sample size calculation

During a week period all patients meeting the inclusion and exclusion criteria will be recruited. Based on current rates of admissions in the mentioned services, we expect to recruit at least 6 patients during a week data collection period.

### 1.2 Study period

The enrollment period will last a week. Demographic and baseline clinical data are recorded on admission while outcome data are captured at hospital discharge. The hospital discharge of the last patient enrolled will be considered the end of the data collection period for this study. The study period will end at completion of data analysis.

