#### 6.1.2 Procedure

1. Weigh neonate if weight is > 800 < 2000, and neonate has stable breathing document initial assessment and obtain informed consent from parent
2. Fill the plastic bottle with boiled water and put it in the incubator. We boil clean water by our electric kettle.
3. Assemble incubator
4. Place the bottle in the foil wrap and secure in designated position in the incubator at each end

5. Use hygrometer to confirm that internal incubator temperature is greater than 32 degrees Celsius and less than 37 degrees Celsius.
6. Place neonate inside incubator ensure they are stable.
7. Use data collection sheet to assess each parameter every **15 minutes for the 1st hour** if the baby is stable (maintain the baby's temperature and not change the breathing condition) , we measure the parameter **every 30 minutes**. If the temperature in the incubator exceeds 37° ,open the incubator for 5 minutes and measure the temperature again.
8. Newborn in the incubator always wear a pulse oximeter.
9. Measure without opening the incubator
10. We follow the ODCH doctor's instructions for the interval and methods of feeding.
11. Local nurses observes the newborn in an incubator for 24 hours and then return the newborns to cot.
12. Call a local medical doctor if the newborn has the following problems during our monitoring.: 1) the newborn's respiratory condition deteriorates, 2) the newborn has problem with their feeding patterns and vital signs.
13. Change the hot water to keep the newborn's temperature between 36.5°C and 37.2°C.
14. Wipe once a day with clean water. When replacing the newborn, disassemble the incubator and disinfect with alcohol.
15. measure the water temperature.

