## **7.2 Statistical analysis**

This study only records biological parameters and temperature. If we get past neonatal mortality data at Ola During Children's Hospital , we compare the survival rates using Kaplan-Meier method.

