### **8.6 Temporary halt and (prematurely) end of study report**

In the unlikely event of a temporary halt or early stopping of the study, the investigator/sponsor will notify the accredited EC of the end of the study within a period of 8 weeks. The end of the study is defined as the last patient included. The investigators will notify the EC immediately of a temporary halt of the study, including the reason of such an action. In case the study is ended prematurely, the investigators will notify the accredited EC within 15 days, including the reasons for the premature termination. Within one year after the end of the study, the investigators will submit a final study report with the results of the study, including any publications/abstracts of the study, to the accredited EC.

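### Data collection closes at the discharge of the infant enrolled last, so infants enrolled earlier who stay longer have no discharge outcome recorded

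*Protocol*

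**What the plan says.** The Study period section (numbered 1.2 in the body, 5.3 in the contents list) contains three statements that bear on this point:

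- Enrolment: "The enrollment period will last a week".
- Timing of the outcome: "outcome data are captured at hospital discharge", which is a rule for each infant.
- Closure: "The hospital discharge of the last patient enrolled will be considered the end of the data collection period for this study", which is a single date for the whole study, fixed by one infant.

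The same section lets the study period run until the analysis is complete. Section 8.6 defines the end differently: "The end of the study is defined as the last patient included".

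On numbers, the sample size section says "we expect to recruit at least 6 patients during a week data collection period". Table 1 admits "Newborns from 800g to 2000g". Section 6.1.2 fixes the time in the device: "Local nurses observes the newborn in an incubator for 24 hours and then return the newborns to cot".

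The outcome at discharge matters most for section 7.2, where, if past mortality data from the hospital can be obtained, "we compare the survival rates using Kaplan-Meier method". No section says that collection stays open until every enrolled infant has left hospital.

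**The concern.** The closing date follows order of enrolment, whereas outcomes become available in order of discharge. In a trial that recruits over a long period the two orders largely agree, and the wording would do little harm. Here all entries fall within seven days and the weight range is wide. Stays can plausibly differ between infants by more than their entry dates do, although the protocol gives no figure for this.

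An infant who entered early and stays long would then be without a recorded discharge outcome, and a death after closure would not be seen. With about six infants, one or two missing outcomes are a large share of the data. Section 6.4.6 adds to the doubt: it records adverse events and deaths during a period that it does not define. If that period is the data collection period, the same date also limits the recording of deaths.

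**Working it through.** The protocol has no figure to reproduce: it gives no length of stay, and the six infants are an admissions forecast. The check applies the written rule to assumed stays.

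**Inputs from the protocol.** Six infants, a 7-day enrolment period, closure at the discharge of the infant enrolled last, 24 hours in the incubator.

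**Assumptions.** Entry times uniform over the 7 days; stays independent and gamma distributed, with mean 2, 7, 14 or 28 days and coefficient of variation (CV) 0.3, 0.5 or 1.0.

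**Rule.** Let infant *i* enter at *t_i* and stay *L_i*, with infant 6 enrolled last. Infant *i* is cut off when *t_i + L_i > t_6 + L_6*, that is, when *L_i − L_6 > t_6 − t_i*. The right-hand side is at most 7 days. So an infant is cut off whenever its stay exceeds that of the last-enrolled infant by more than the gap between their entries.

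**Results** (200,000 simulated studies per row):

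| Mean stay (days) | CV | Chance at least one infant is cut off | Mean number cut off, of 5 | Chance any 24-hour observation is cut |
|---|---|---|---|---|
| 2 | 0.3 | 24% | 0.29 | 0.2% |
| 2 | 0.5 | 35% | 0.46 | 2.6% |
| 2 | 1.0 | 53% | 0.81 | 11.2% |
| 7 | 0.3 | 54% | 0.97 | 0.0% |
| 7 | 0.5 | 66% | 1.36 | 0.1% |
| 7 | 1.0 | 75% | 1.69 | 4.2% |
| 14 | 0.3 | 69% | 1.55 | 0.0% |
| 14 | 0.5 | 75% | 1.86 | 0.0% |
| 14 | 1.0 | 80% | 2.04 | 2.3% |
| 28 | 0.3 | 76% | 1.99 | 0.0% |
| 28 | 0.5 | 79% | 2.18 | 0.0% |
| 28 | 1.0 | 81% | 2.25 | 1.2% |

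Repeat runs of the last row give 81% to 82%, so the range is quoted as 24% to 82%.

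**Upper limit.** If stays are exchangeable and entry gaps are negligible beside them, each infant is equally likely to leave last. The chance of a cut-off is then 1 − 1/6 = 5/6 = 83%, and the mean number is 5 × 1/2 = 2.5.

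**Hand check of the CV 1.0 rows.** These stays are exponential with mean *m*. The last of six uniform entries falls on average at 7 × 6/7 = 6 days. An earlier infant is still in hospital then with probability of about (*m*/6)(1 − e^(−6/*m*)), and by the memoryless property outstays the last infant half the time.

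- *m* = 28: (28/6)(1 − 0.807) = 0.900, and 5 × 0.900/2 = 2.25, against 2.25 simulated.
- *m* = 7: (7/6)(1 − 0.424) = 0.672, and 5 × 0.672/2 = 1.68, against 1.69 simulated.

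**Length of enrolment.** Apart from the 24-hour column, the result depends only on the ratio of mean stay to enrolment period. The project summary mentions two weeks of data collection as well as one. If enrolment took two weeks, a mean stay of 14 days would behave like the 7-day rows above, and 28 days like the 14-day rows.

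**After the fix.** If collection closes when the last infant remaining has been discharged or has died, none of the six is cut off, whatever the stays.

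**The case against.** The strongest reply is that this is only loose wording. The preceding sentence sets a rule for each infant, and the writers may have meant the last discharge among all enrolled infants. That may well be the intent, but the sentence does not say it, no other section does, and section 8.6 points to an earlier date. If it was the intent, the fix merely writes it down.

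Several stronger readings are tempting, and the protocol does not support them:

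- **That survival is necessarily biased upwards.** An infant's cut-off depends on entry dates and on another infant's stay, not on its own prognosis. If stays are independent, that is administrative censoring, which Kaplan-Meier can handle. Survival is clearly overstated only if infants cut off are counted as survivors, and the protocol does not plan that. What is certain is a loss of information on the longest stayers.
- **That the main results are at risk.** The data sheet runs to 360 minutes and incubator observation lasts 24 hours. The chance that any 24-hour observation is cut is 0% to 4% for mean stays of 7 days or more, and at most 11% in the 2-day rows.
- **That the only planned comparison is damaged.** Section 4.1.2 also plans to compare temperature inside and outside the incubator. The survival comparison is conditional on historical data, and survival is not a stated objective or hypothesis.
- **That loss is near certain, at about 74% to 82%.** Those figures need long or highly variable stays and are only the upper part of the range.
- **That the infants lost are the sickest.** Breathing disorders, sepsis and fatal congenital disease are excluded at entry, and the protocol has no data linking stay to severity in those who remain.
- **That no closing date exists if the infant enrolled last dies.** A death also ends the hospital stay on a known date, so closure could be dated. The wording should still name death.

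**Conclusion.** The point holds as a defect in a stated rule. Followed literally, the Study period section closes collection before some infants may have reached the discharge at which their outcome is to be captured, and section 8.6 sets an end of study that is earlier still. For mean stays of 2 to 28 days the chance that at least one of six infants is affected is about 24% to 82%, with 0.3 to 2.3 infants affected on average. These figures rest on assumed, independent stays and uniform entry over one week. They illustrate the size and are not estimates for this hospital.

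The consequence is limited to discharge outcome and late deaths, and hence to the conditional survival comparison in section 7.2. The correction is worth making because it is cheap and the missing outcomes cannot be recovered within the study once collection has closed.

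**What to change.** Three changes:

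1. In the Study period section, replace the closing rule with: *Data collection ends when every enrolled infant has been discharged or has died.*
2. Define the outcome recorded for each infant as vital status at discharge or in-hospital death, with its date.
3. Bring the end-of-study definition in section 8.6 into line with this, so that the notification and reporting deadlines there run from the same date.

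The cost is two amended passages and one dated entry per infant, with no added procedure. The file may, however, stay open beyond the February 2020 data collection month in section 8.4, and so into the March to April analysis period. Purely as an illustration, if an 800 g infant stayed until reaching an assumed 1800 g at an assumed gain of 15 to 25 g per day, the stay would be 1000/25 = 40 to 1000/15 = 67 days. The timeline should allow for this. Analysis of the temperature and vital-sign data need not wait for it.

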## 6. METHODS

### 6.1. Study parameters/endpoints

#### 6.1.1 Main study parameter

i . (Incubator) Measure the following parameters .(SpO2, HR, respiratory rate, Blood temperature, incubator inside temperature, incubator outside temperature, water temperature, incubator inside oxygen concentrate, milk intake, incubator inside humidity, incubator outside humidity)

	SpO2	HR	RR	BT(armpit)	incubator inside temperature	incubator outside temperature	water temperature	incubator inside oxygen concentrate	milk intake(ml)	incubator inside humidity	incubator outside humidity
pre implementation											
15 minutes											
30											
45											
60											
90											
120											
150											
180											
210											
240											
270											
300											
330											
360											

#### 6.1.2 Procedure

1. Weigh neonate if weight is > 800 < 2000, and neonate has stable breathing document initial assessment and obtain informed consent from parent
2. Fill the plastic bottle with boiled water and put it in the incubator. We boil clean water by our electric kettle.
3. Assemble incubator
4. Place the bottle in the foil wrap and secure in designated position in the incubator at each end

5. Use hygrometer to confirm that internal incubator temperature is greater than 32 degrees Celsius and less than 37 degrees Celsius.
6. Place neonate inside incubator ensure they are stable.
7. Use data collection sheet to assess each parameter every **15 minutes for the 1st hour** if the baby is stable (maintain the baby's temperature and not change the breathing condition) , we measure the parameter **every 30 minutes**. If the temperature in the incubator exceeds 37° ,open the incubator for 5 minutes and measure the temperature again.
8. Newborn in the incubator always wear a pulse oximeter.
9. Measure without opening the incubator
10. We follow the ODCH doctor's instructions for the interval and methods of feeding.
11. Local nurses observes the newborn in an incubator for 24 hours and then return the newborns to cot.
12. Call a local medical doctor if the newborn has the following problems during our monitoring.: 1) the newborn's respiratory condition deteriorates, 2) the newborn has problem with their feeding patterns and vital signs.
13. Change the hot water to keep the newborn's temperature between 36.5°C and 37.2°C.
14. Wipe once a day with clean water. When replacing the newborn, disassemble the incubator and disinfect with alcohol.
15. measure the water temperature.

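### The recording table for the main study parameter ends at 360 minutes, while the infant stays in the incubator for 24 hours under a reading schedule with no stated end

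*Protocol*

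**What the plan says.** Section 6.1.1 of the Protocol introduces the main study parameter with the words "Measure the following parameters" and a blank table. Its rows are a pre-implementation reading, then 15, 30, 45 and 60 minutes, then each half hour from 90 to 360 minutes. Its columns include armpit temperature and the temperatures inside and outside the incubator.

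Section 6.1.2 gives the procedure:
- Step 7 tells staff to use the data collection sheet, with readings each quarter hour in the first hour. After that, "if the baby is stable (maintain the baby's temperature and not change the breathing condition) , we measure the parameter" "every 30 minutes". No end time is given.
- Step 8: "Newborn in the incubator always wear a pulse oximeter".
- Step 11: the local nurse "observes the newborn in an incubator for 24 hours and then return the newborns to cot".
- Step 13: "Change the hot water to keep the newborn's temperature between 36.5°C and 37.2°C". No time limit is given here either.

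The primary hypothesis (section 4.1.3) is that the infant's temperature stays constant, with no time window. Section 7.1.2 has data written on paper forms and then transcribed to an electronic form. Section 7.2 says that the study records only biological parameters and temperature.

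**The concern.** The table and the procedure describe different lengths of measurement for the same quantities. One nurse could stop writing at 360 minutes because the table ends there. Another could continue to 24 hours because step 7 does not say to stop. Both would be following the Protocol, and they would produce different data on the main parameter.

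These readings are the study's result, and section 5 (sample size) expects only about 6 infants. If later readings are kept for some infants and not for others, the record after 6 hours depends on individual choice. If they are kept for none, the hypothesis of constant temperature is examined over a quarter of the stay. The secondary hypothesis (section 4.1.4), that the inside temperature holds whatever the temperature outside, draws on columns of the same table, and a 6-hour record cannot span a full day. Because the electronic form is filled from paper, a reading with no place on the paper may never reach the dataset, and no later analysis plan can recover it.

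**Working it through.** **Inputs**
- Last row of the table: 360 minutes (section 6.1.1).
- Stay in the incubator: 24 h = 1440 minutes (section 6.1.2, step 11).
- Reading interval: 15 minutes up to 60 minutes, then 30 minutes if the infant is stable (section 6.1.2, step 7).

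**Reproducing the printed table.** Apply step 7 up to 360 minutes:
- First hour: 60 / 15 = 4 readings.
- 60 to 360 minutes: (360 − 60) / 30 = 10 readings.
- With the pre-implementation row: 1 + 4 + 10 = 15 rows.

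These are exactly the times printed in section 6.1.1. The Protocol does not expressly call this table the data collection sheet of step 7, but the exact match makes that the natural reading.

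**Running the same schedule to the end of the stay**
- 60 to 1440 minutes: (1440 − 60) / 30 = 46 readings.
- Total: 1 + 4 + 46 = 51 rows.

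**Comparison**

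| | Needed for 24 h | Printed | No row |
|---|---|---|---|
| Rows, including pre-implementation | 51 | 15 | 36 (36/51 = 71%) |
| Time in incubator | 24 h | 6 h | 18 h (1080/1440 = 75%) |

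The 36 readings without a row run from 390 to 1440 minutes.

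**Assumption.** The count of 51 is for an infant who is stable throughout, since step 7 attaches the 30-minute interval to that condition. It does not give the interval otherwise. The 18 hours do not depend on this.

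**Search for a reconciling statement.** Sections 1, 4, 6.1 and 7 do not say that readings stop at 360 minutes, that the table is one page of a repeated sheet, or which time window the primary result covers.

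**The case against.** The strongest reply is that later readings are in fact planned. Step 7 has no end time, step 8 keeps a pulse oximeter on the infant, step 11 has a nurse observing for the whole 24 hours, and step 13 cannot be followed without continued temperature checks. The project summary also promises monitoring round the clock. The printed grid could be one page of a sheet used repeatedly, since section 7.1.2 speaks of forms in the plural. Nothing calls the grid the analysis window.

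Most of this stands, and it rules out stronger readings. A reader might infer that hours 6 to 24 have no planned readings, or that the result will describe only the first quarter of use. The documents support neither. A reader might also infer that late hypothermia or overheating would go unrecorded. Sections 6.4.5 and 6.4.6 require all adverse events to be recorded, with no 6-hour cut-off, although an excursion not judged an adverse event could still lack a row.

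Nor do the documents show that the early hours are the favourable ones. They say nothing about time of placement or staff fatigue. The number of hot-water fills in 24 hours cannot be derived either: the laboratory durations in section 6.3.2 and the Appendix are bench results, and step 13 ties water changes to the infant's temperature, not to a clock.

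What the reply does not do is settle the contradiction. An oximeter does not measure body or incubator temperature. Checks made to manage the water need not be written down as study data. Reuse of the sheet is possible but nowhere stated. The choice of analysis window might be left to a statistical analysis plan, but what is recorded, and until when, is fixed in the Protocol.

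**Conclusion.** The point holds as an unresolved contradiction about what is recorded for the study's only main parameter. Taking step 7 at its word for a stable infant over the stay in step 11, 36 of 51 scheduled readings and 18 of 24 hours have no row in the table. It is therefore unclear whether those hours are recorded and count towards the primary result, and a claim of constant temperature during use could rest on the first 6 hours only. That outcome is possible, not certain: it depends on how staff resolve the mismatch, which the Protocol leaves open. The conclusion rests on reading the section 6.1.1 table as the sheet meant in step 7. It should be settled before enrolment, because readings not written down cannot be recovered.

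**What to change.** Reconcile sections 6.1.1 and 6.1.2 in one of two ways.

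- If measurement is meant to last the whole stay, extend the table to 1440 minutes at the interval step 7 already sets (51 rows), or state that the sheet is repeated with running times. Also state that the main parameter covers the full 24 hours.
- If only 6 hours of study measurement is intended, give step 7 that end time, and state in sections 4 and 7.2 that the conclusions are limited to the first 6 hours in the incubator.

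The first option costs a longer paper form and 36 more rows of data entry per infant, about 216 for the 6 infants expected (36 × 6). It adds no new readings, since step 7 sets no end to them and step 11 already has nurses observing. The second costs a sentence or two and a narrower claim.

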#### **6.1.4 Randomization, blinding and treatment allocation**

Patients are prospectively recruited on a consecutive basis. No randomization will be performed.

#### **6.2. Study groups**

Not applicable.

#### **6.3. Study procedures**

##### **6.3.1 Study procedures**

##### **6.3.2 Intervention**

##### **(incubator)**

This product was developed by ATOM and IGPC as shown in Appendix. The incubator is made of vinyl and water tank made of plastic. The mattress uses thermal insulation to prevent direct contact with the newborn. In experiments, we have confirmed that incubators can be kept warm for more than 3 hours with a single hot water change. Also in the experiment, the temperature of the doll's surface did not become so high as to cause burns.

#### **6.4. Safety consideration and follow up**

##### **6.4.1 Withdrawal of individual subjects**

Patients can leave the study at any time for any reason if they wish to do so without any consequences. The investigator can decide to withdraw a subject from the study for urgent medical reasons.

The study participants have the right to contact the ethics and review committee if they raise any issue or concern with the study (Office of the Sierra Leone Ethics and Scientific Review Committee, Ministry of Health and Sanitation, Directorate of Policy, Planning & Information (DPPI) [name]).

